### Matched Cohort

A matched propensity score analysis will be used to assess comparative persistence between the two exposure comparison groups. Logistic regression will be used to calculate the propensity to initiate Olodaterol/Tiotropium Bromide versus Umeclidinium/Vilanterol given all covariates (except components of the Charlson Comorbidity index) listed in [section 9.3.3](#), according to the following model:

$$\text{Logit}(\text{Treatment} | X_1, X_2, \dots, X_n) = \beta_0 + \beta_1 * X_1 + \beta_2 * X_2 + \dots + \beta_n * X_n$$

Any covariates which are collinear with each other will be dropped from the analysis (if it causes failure of model to converge). The propensity score will then be used to identify up to 2 initiators of Umeclidinium/Vilanterol for each initiator of Olodaterol/Tiotropium Bromide with the same propensity score ( $\pm$  a caliper of 5%) as the corresponding initiator of Olodaterol/Tiotropium Bromide (Austin 2011).

## 9.3 VARIABLES

### 9.3.1 Exposures

- Exposure: Olodaterol/Tiotropium Bromide (Stiolto®) delivered with Respimat inhalator
- Active Comparator: Umeclidinium/Vilanterol (Anoro®) delivered with the Ellipta Inhaler

Both exposures will be identified via NDC Generic Name and NDC Brand Name.

### 9.3.2 Outcomes

#### 9.3.2.1 Primary outcome

##### Discontinuation

The primary outcome of interest is discontinuation of index treatment (Olodaterol/Tiotropium Bromide or Umeclidinium/Vilanterol), defined as persistence (i.e. no refill claim within 60

days [not involving treatment switch, nor death] (allowable grace period) after end of <n> days supply) during follow-up.

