## Protocol for non-interventional studies based on existing data

Document Number:	c30445781-01
BI Study Number:	1237-0090
BI Investigational Product(s):	Stiolto® Respimat®
Title:	The Role of Inhaler Device in the Treatment Persistence with Dual Bronchodilators in Patients with COPD
Protocol version identifier:	1.0
Date of last version of protocol:	N/A
PASS:	No
EU PAS register number:	Study not registered
Active substance:	Olodaterol and Tiotropium Bromide (ATC R03AL06) Umeclidinium and Vilanterol (ATC R03AL03)
Medicinal product:	Stiolto® Respimat®; Anoro® Ellipta®
Product reference:	N/A
Procedure number:	N/A
Joint PASS:	No
Research question and objectives:	
The primary objective of the study is to use US data to determine relative persistence between Olodaterol/Tiotropium Bromide delivered with the Respimat soft mist inhaler and Umeclidinium/Vilanterol delivered with the Ellipta dry powder inhaler using a 1:2 propensity score matched analysis.
 
The secondary objectives of the study are as follows:
 
 
- Characterize new users of Olodaterol/Tiotropium Bromide and Umeclidinium/Vilanterol in terms of demographics, medication use, comorbidities, and other variables, before and after propensity score matching.
 
- Determine the incidence rate and proportion of patients discontinuing or switching among new users of Olodaterol/Tiotropium Bromide and Umeclidinium/Vilanterol.
 
- Determine the relative rate and proportion of patients discontinuing between Olodaterol/ Tiotropium Bromide and
 

	Umeclidinium/Vilanterol. using a standard multivariate analysis (If feasible).
Country(-ies) of study:	United States
	T: Email:
Author:	T: Email:
	BI contact person:
Marketing authorisation holder(s):	
MAH contact person:	
In case of PASS, add:	N/A
In case of PASS, add:	N/A
Date:	22 November 2019
Page 1 of 69	
Proprietary confidential information © 2019 Boehringer Ingelheim International GmbH or one or more of its affiliated companies. All rights reserved. This document may not - in full or in part - be passed on, reproduced, published or otherwise used without prior written permission	

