
Variables:
 
Exposures
 
 
• Olodaterol/Tiotropium Bromide (Stiolto®) delivered via Respimat inhaler
 
• Umeclidinium/Vilanterol (Anoro®) delivered via Ellipta Inhaler
 
 
Outcome
 
 
• Discontinuation of index treatment (Olodaterol/Tiotropium Bromide or Umeclidinium/Vilanterol), defined as persistence of treatment (no refill claim within 60 days (allowable grace period) after end of <n> days supply). Addition of another drug will not count as a discontinuation.
 
 
Covariates
 
Demographics
 
 
• Age on the cohort entry date
 
• Sex (Male, Female)
 
• Region (Northeast, North Central, South, West, Unknown, Missing)
 
• Insurance Type (Commercial, Medicare, Missing)
 
• Study Year of Cohort Entry (First Year: 17 Nov 2015-30 Nov 2016, Second Year: 01 Dec 2016-30 Nov 2017, Third Year: 01 Dec 2017-31 Mar 2018)
 
 
Concomitant Medications
 
 
• Oral Corticosteroids (OCS)
 
• Short acting muscarinic antagonist (SAMA)
 
• Short acting beta agonist (SABA)
 
• Long acting muscarinic antagonist (LAMA)
 
• Long acting beta agonist (LABA)
 
• Inhaled corticosteroid (ICS)
 
• LAMA / LABA combination (that is not Stiolto or Anoro)
 
• LABA / ICS combination
 
• LAMA / LABA / ICS combination
 
• NSAIDs
 
• Antihistamines
 
			

Name of company: Boehringer Ingelheim International GmbH			
Name of finished medicinal product: Stiolt® Respimat®; Anoro® Ellipta®			
Name of active ingredient: Olodaterol and Tiotropium Bromide (ATC R03AL06); Umeclidinium and Vilanterol (ATC R03AL03)			
Protocol date: 22 November 2019	Study number: 1237-0090	Version/Revision: 1.0	Version/Revision date: NA

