Name of company: Boehringer Ingelheim International GmbH			
Name of finished medicinal product: Stiolto® Respimat®; Anoro® Ellipta®			
Name of active ingredient: Olodaterol and Tiotropium Bromide (ATC R03AL06); Umeclidinium and Vilanterol (ATC R03AL03)			
Protocol date: 22 November 2019	Study number: 1237-0090	Version/Revision: 1.0	Version/Revision date: NA
Data sources:	Truven MarketScan is a claims database that captures longitudinal, individual-level administrative claims data from the United States.		
Study size:	There are 14,751 new users of Olodaterol/Tiotropium Bromide or Umeclidinium/Vilanterol between 17 November 2015 and 31 March 2018 who satisfied the inclusion criteria. Among them, 3,889 initiated Olodaterol/Tiotropium Bromide and 10,862 initiated Umeclidinium/Vilanterol).		
Data analysis:	
For demographic and lifestyle variables, the value recorded on the cohort entry date will be reported, otherwise the most recent known value will be reported. Presence of comorbidities and use of concomitant medication use will be determined based whether they ever occurred within the 180-day baseline period preceding the index date. Differences in the confounder distributions will be inspected for successful confounder balance of measured characteristics.
 
Patients will be followed up until first occurrence of death, discontinuation, disenrollment, end of data, or 365 days.
 
The data will be displayed in a nonparametric fashion on a persistency curve (a Kaplan–Meier curve) with discontinuation considered as elimination.
 
Unmatched Cohort Rates and risks (proportion of patients) with the outcomes for each exposure group will be reported among the unmatched cohort.
 
Matched Cohort Rates and risks (proportion of patients) with the outcomes for each exposure group will be reported among the matched cohort.
 
Logistic regression will be used to calculate the propensity to initiate Olodaterol/Tiotropium Bromide versus Umeclidinium/Vilanterol. The propensity score will then be used to identify up to 2 initiators of Umeclidinium/Vilanterol for each initiator of Olodaterol/Tiotropium Bromide with the same propensity score (<math>\pm</math> a caliper of 5%) as the corresponding initiator of Olodaterol/Tiotropium Bromide.
		

Name of company: Boehringer Ingelheim International GmbH			

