### **9.2 SETTING**

#### **9.2.1 Definitions**

Study Period: the period of time that includes the exclusion criteria assessment period, baseline, cohort entry date, and follow-up period for the study population. This period is the same for all patients.

The study period will be from 1 January 2008 to 31 March 2018, encompassing date of the earliest data availability to the date of the latest data availability.

Patient Selection Period: the period of time for which patients are eligible to enter the cohort. The earliest date of the patient selection period is 17 November 2015, corresponding to 180-days after US approval date of Stiolto Respimat.

Cohort Entry Date: Date of entry to the initial cohort of Stiolto or Anoro users.

[figure not shown]
Baseline Period: the 180-day period that ends 1 day prior to the cohort entry date used to assess covariate information. The baseline period will vary between patients depending on these dates. The earliest start of the baseline period would be 21 May 2015, the date of Stiolto approval (i.e. 180 days before November 17, 2015).

Follow-Up Period: the period of time between 1 day after the cohort entry date to the earliest occurrence of the outcome (discontinuation of refills), or any censoring criteria (365 days, death, disenrollment, or end of data). Addition of another treatment in addition to index treatment will not count as discontinuation.

For entry into the study population, patients will be required to have 180 days of continuous enrolment with both medical and pharmacy coverage. Data during the baseline period will be used to confirm study eligibility and classification of incident COPD. The follow-up period will be used for capturing first and second maintenance therapies. This is illustrated in **Figure 1**.

Figure 1

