#### **Censoring**

Patients will be censoring if they did not discontinue their index treatment but had an occurrence of any of the following: 365 days of follow-up without discontinuation, death, disenrollment, end of data.

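### The primary outcome has no single rule for patients who switch inhaler: section 9.3.2.1 removes a switch from discontinuation, no censoring list names it, and the Abstract and 9.2.1 would count it as an event

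*Combined protocol and SAP*

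**What the plan says.** The statements on the event and on the end of follow-up are these.

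- **Section 9.3.2.1, Discontinuation.** The event is no refill claim within 60 "days [not involving treatment switch, nor death] (allowable grace period) after end of <n> days supply) during follow-up". Both a switch and death are carved out.
- **Section 9.3.2.1, Censoring.** The list is "365 days of follow-up without discontinuation, death, disenrollment, end of data". Death appears; switch does not.
- **Section 9.2.1, Follow-Up Period.** Follow-up runs to "the earliest occurrence of the outcome (discontinuation of refills), or any censoring criteria (365 days, death, disenrollment, or end of data". The only exemption is "Addition of another treatment in addition to index treatment will not count as discontinuation".
- **Abstract, Outcome.** The event is "no refill claim within 60 days (allowable grace period) after end of" the days of supply, with no mention of switching. The only exemption is "Addition of another drug will not count as a discontinuation".
- **Abstract, Data analysis.** "Patients will be followed up until first occurrence of death, discontinuation, disenrollment, end of data, or 365 days". Switch is again absent.
- **Title page, secondary objectives.** "Determine the incidence rate and proportion of patients discontinuing or switching among new users". The matching objectives in the Abstract and in section 8 refer to discontinuation only, and section 9.3.2.2 defines no secondary outcomes.

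No section says what a switch is: which products count, over what time window, or how it differs from add-on therapy.

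**The concern.** Discontinuation is the study's only outcome, and the study asks whether the inhaler device affects persistence. A patient who gives up the index device for another product is central to that question, yet the documents support three different codings of that patient:

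1. **Event**, under the Abstract and 9.2.1, because the index refills stopped and only add-on therapy is exempt.
2. **Censored at the switch**, if the bracket in 9.3.2.1 is meant to treat a switch like death. This is not written anywhere.
3. **Still at risk and persistent**, if 9.3.2.1 and its censoring list are followed as written. There is no event and no censoring date, so the patient accrues time until day 365 or earlier death, disenrollment or end of data.

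The third reading scores leaving the device as persistence with it. The primary matched analysis is a Cox model with treatment as its only term (9.7.1.3), so the coding passes straight into the hazard ratio. The risks in 9.7.1.2 divide events by patients at entry, so they move too. None of the four sensitivity analyses in 9.7.2 varies the handling of switches, so the reported results would not reveal the choice.

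**Working it through.** **Text check.** For a patient who replaces the index inhaler and never refills it:

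| Source | Event? | Follow-up ended by the switch? |
|---|---|---|
| Abstract, Outcome and Data analysis | Yes (no refill; only add-on exempt) | Yes, as the event |
| 9.2.1 | Yes (refills discontinued; only add-on exempt) | Yes, as the event |
| 9.3.2.1 with its censoring list | No (carved out) | No (switch not listed) |

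Death is carved out of the event and also listed as censoring. Switch is carved out and listed nowhere.

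**Illustration of size.** The documents give no switching rate, discontinuation rate or matched sample size, so there is no plan figure to reproduce. The rates below are assumptions.

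Inputs:
- One-year non-persistence of 60% (assumed), with constant hazards: L = −ln(1 − 0.60) = 0.916 per year.
- Entry assumed uniform over 17 November 2015 to 31 March 2018 (866 days, inclusive). Data end on 31 March 2018 (9.2.1), so 365/866 = 42% of entry dates cannot reach day 365.
- Arms in ratio 1:2; a = stopping hazard, b = switching hazard; subscript 1 is the index arm and 0 the comparator.

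Formulas:
- Switch as event: HR = (a₁ + b₁)/(a₀ + b₀).
- Switch censored: HR = a₁/a₀.
- Switcher kept at risk: no closed form; the large-sample Cox score equation was solved numerically.

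| Scenario (a₁/b₁ vs a₀/b₀, in units of L) | Event | Censored | Kept at risk |
|---|---|---|---|
| Same total, switch share 10% vs 20%: 0.9/0.1 vs 0.8/0.2 | 1.0/1.0 = 1.00 | 0.9/0.8 = 1.125 | 1.173 |
| Shares reversed: 0.8/0.2 vs 0.9/0.1 | 1.00 | 0.8/0.9 = 0.889 | 0.852 |
| Same total, share 10% vs 15%: 0.9/0.1 vs 0.85/0.15 | 1.00 | 0.9/0.85 = 1.059 | 1.082 |
| Same total, share 10% vs 12.5%: 0.9/0.1 vs 0.875/0.125 | 1.00 | 0.9/0.875 = 1.029 | 1.040 |
| Same stopping, threefold switching: 0.8/0.1 vs 0.8/0.3 | 0.9/1.1 = 0.818 | 1.00 | 1.090 |
| Same stopping, twofold switching: 0.8/0.1 vs 0.8/0.2 | 0.9/1.0 = 0.900 | 1.00 | 1.045 |
| Same stopping, 1.25-fold switching: 0.8/0.1 vs 0.8/0.125 | 0.9/0.925 = 0.973 | 1.00 | 1.011 |

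**Equal stopping and switching in both arms.** The HR is 1.00 under every rule. The reported risk still moves: with switching at 10% or 20% of non-persistence, the full-year risk falls from 0.60 to 0.9 × 0.60 = 0.54 or 0.8 × 0.60 = 0.48 once a switch is no longer an event. With the end-of-data cut-off applied, the proportion of entrants falls from 0.493 to 0.443 or 0.394.

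**Scale against sampling error.** Section 9.5 gives 3,889 index initiators. Matching is to up to two comparators within a caliper, so the matched set is at most 3,889 + 7,778. The 95% CI factor each way is exp(1.96 × √(1/(n₁e) + 1/(n₀e))), with e the assumed event proportion:

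| n₁ + n₀ | e = 0.4 | e = 0.6 |
|---|---|---|
| 3,889 + 3,889 | 1.073 | 1.059 |
| 3,889 + 7,778 | 1.063 | 1.051 |

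The twofold and threefold contrasts move the HR between rules by more than this factor. The 1.25-fold contrasts do not.

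**The case against.** Only 9.3.2.1 speaks explicitly about a refill gap involving a switch. The Abstract and 9.2.1 never state that a switch is an event; that follows from an unqualified no-refill definition whose sole exemption is add-on therapy. The short forms could be read as deferring to the dedicated outcome section. Section 9.2.1 also says that follow-up serves to capture first and second maintenance treatments, and the title page names switching apart from discontinuing. Both hint that the carve-out was deliberate. Discontinuation with switches censored is a coherent estimand, and the documents do not settle which was meant. Finally, the larger shifts need a two- or threefold difference in switching between arms.

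Some of this stands. Intent is open, and the numerical effect may be small: the 1.25-fold rows stay inside the CI factor. It does not remove the defect. Section 9.2.1 is body text, so the conflict is not just Abstract against body. Its line on maintenance treatments sets neither an event nor a censoring rule. If the carve-out is deliberate, the plan still lacks any rule for ending the switcher's follow-up, and the literal result is the reading least suited to a persistence study.

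**Conclusion.** The concern holds and must be fixed before the outcome is coded. The contradiction and the missing censoring rule are shown by the text alone and need no assumed rates.

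The size is illustrative, under constant hazards, 60% one-year non-persistence and uniform entry. When switching differs two- to threefold between arms, the choice of rule moves the primary HR by about 16% to 33% between the extreme readings (1.045/0.900 = 1.16; 1.090/0.818 = 1.33) and can put it on the other side of 1. With a 1.25-fold difference the shift is about 4% (1.040/1.000 = 1.04; 1.011/0.973 = 1.04). With equal stopping and switching the HR does not move, but the reported one-year risk drops by 6 to 12 percentage points if switching is 10% to 20% of non-persistence.

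The title-page mention of switching is a smaller, separate misalignment and adds nothing to the severity.

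**What to change.** 1. Define switch: the products that count, the time window relative to the end of supply, and how it differs from add-on therapy.
2. Write one rule and use it in the Abstract (Outcome and Data analysis), 9.2.1, and both the outcome and censoring paragraphs of 9.3.2.1. The rule that best fits the Abstract, 9.2.1 and the persistence question is to delete the switch exclusion from 9.3.2.1. Any failure to refill the index product within the grace period is then an event, whether or not another product was started. Added therapy with continued index refills remains a non-event.
3. Report stopped and switched patients separately as description, and add one sensitivity analysis that censors at the switch or treats it as a competing event.
4. If the sponsor does mean to exclude switches from the event, add switch to all three end-of-follow-up lists and to the Abstract definition. State also how switchers enter the events-per-patient risks and the logistic models.
5. Align the title-page secondary objective with those in the Abstract and section 8.

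The cost is wording in these places, one outcome algorithm and one extra sensitivity run. No new data are needed.

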## Study timeline for the Primary Study Population

## 9.2.2 Study population

The pre-matched study cohort will consist of patients initiating Olodaterol/Tiotropium Bromide or Umeclidinium/Vilanterol between 17 November 2015 and 31 March 2018.

The following exclusion criteria will then be applied:

Aged <40 years.

Enrolment with medical and pharmacy coverage prior to the cohort entry < 180 days.

Never had COPD diagnosis on the cohort entry date or prior to cohort entry.

A record for dispensed Olodaterol/Tiotropium Bromide delivered with Respimat inhalator or Umeclidinium/Vilanterol delivered with the Ellipta Inhaler during the 180-day baseline prior to cohort entry.

[figure not shown]
Diagnosis of asthma any time prior to cohort entry.

Diagnosis of lung cancer any time prior to cohort entry.

Diagnosis of lung transplant any time prior to cohort entry.

Figure 2

Below depicts the flow diagram of patients.

Diagnosis of COPD (ICD-9: 491.\*, 492.\*, 496.\*; ICD-10: J41.0, J41.1, J41.8, J42.\*, J43.0, J43.1, J43.2, J43.8, J43.9, J44.0, J44.1, J44.9) will be defined as the presence of an inpatient or outpatient claim.

Diagnosis of asthma (ICD-9: 493.\*; ICD-10: J45, J45.20, J45.21, J45.22, J45.90\*, J45.99\*) will be defined as either 1 inpatient claim or 2 outpatient events 30-365 days apart.

Diagnosis of lung cancer (ICD-9: 162.2, 162.3, 162.4, 162.5, 162.8, 162.9, 231.2; ICD-10: C34.00, C34.01, C34.02, C34.10, C34.11, C34.12, C34.2, C34.30, C34.31, C34.32, C34.80, C34.81, C34.82, C34.90, C34.91, C34.92, C7A.090, D02.20, D02.21, D02.22, Z85.118) will be defined as either 1 inpatient claim or 2 outpatient events 30-365 days apart.

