**9.4 DATA SOURCES**

The proposed study will utilize data from Truven MarketScan data (US).

The Truven MarketScan databases capture longitudinal, individual-level administrative claims data from the United States. The data available for the study includes three components of MarketScan: the Commercial Claims and Encounters (CCAE) Database, the Medicare Supplemental and Coordination of Benefits Database (MDCR), and the Medicaid Database. Patients in the databases include active employees, dependents, retirees, COBRA recipients, and Medicare or Medicaid enrollees. Data were drawn from large employers, health plans, and public organizations in the United States. The following tables of the MarketScan databases were available for analysis: Enrollment Detail, Inpatient Admissions, Inpatient Services, Outpatient Services, Outpatient Pharmaceutical Claims, and Long Term Care. These tables provide information on plan enrollment, healthcare utilization and expenditures, demographics, and integrated records for inpatient events, outpatient events, and pharmacy dispensings. Data are available from January 1, 2008 to March 31, 2018, and represent approximately 162 million patients.

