### 9.7.2 Sensitivity Analysis

Four sensitivity analyses will be conducted. For these analyses, in the interest of reducing the number of additional tables, only the descriptive statistics for the matched population ([Annex Table 2](#)), and primary results ([Annex Tables 4](#) and [5](#)) will be reported.

Two sensitivity analyses will be conducted to evaluate the robustness of the outcome definition:

1. Use of a 30-day Grace Period

Restrict the 60-day allowable grace period used to define the discontinuation outcome to 30 days to allow a gap of one month. This sensitivity analysis may be useful if the 60-day grace period is too lenient, as the usual day's supply of Stiolto is 30 days.

2. Use of a 90-day Grace Period

Since neither the Olodaterol/Tiotropium Bromide or Umeclidinium/Vilanterol drug products are available as generic formulations, the relatively high price of these medications may lead some patients to space out their doses to greater than the recommended dosing schedule or use one puff instead of two to prolong their medication supply. Patients may also neglect to take their medications due to forgetfulness or because they become less symptomatic. Thus, we will also increase the 60-day allowable grace period used to define the discontinuation outcome, to 90 days.

Two sensitivity analyses will be conducted in an attempt to increase the sample size:

3. Start Patient Identification Period in 21 May 2015

The primary identification period starts 180 days after Stiolto Respimat was approved by FDA for use in the US (21 May 2015) on 17 November 2015. This sensitivity cohort will start the patient identification period immediately upon FDA approval on 21 May 2015.

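### Read literally, the 60-day gap must finish before day 365 or the last data day, and the event is undated, so absolute persistence is overstated; the matched hazard ratio is little affected

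*Combined protocol and SAP*

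**What the plan says.** Section 9.3.2.1 has discontinuation of index treatment "defined as persistence (i.e. no refill claim within 60" days, and continues "allowable grace period) after end of <n> days supply) during follow-up". Section 9.2.1 runs follow-up from the day after cohort entry "to the earliest occurrence of the outcome (discontinuation of refills), or any censoring criteria (365 days, death, disenrollment, or end of data". The Censoring paragraph repeats those limits: "365 days of follow-up without discontinuation, death, disenrollment, end of data".

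Section 9.2.2 admits patients who initiate treatment "between 17 November 2015 and 31 March 2018". Section 9.4 states "Data are available from January 1, 2008 to March 31, 2018". Entry therefore closes on the last data day. Enrolment is required only before entry, and no minimum follow-up is set.

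Section 9.7.1.2 defines risk as events over all eligible patients at entry. In Section 9.7.1.3 the Cox time variable is time to discontinuation, with no statement of which day that is. Section 9.7.2 gives the first sensitivity analysis as "Restrict the 60-day allowable grace period used to define the discontinuation outcome to 30 days"; the second lengthens the period to 90 days. Neither changes the follow-up or censoring rules.

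Sections 9.9 and 9.12 do not mention the problem. The overestimated persistence in Section 9.12 concerns drug that was dispensed but not used.

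**The concern.** A gap-defined event can only be seen once the gap has run. If the gap must finish inside follow-up, a patient whose last supply ends in the final 60 days and who never refills is classed as persistent. This happens at day 365 for patients with full follow-up, and at 31 March 2018 for recent entrants.

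The persistency curve, the discontinuation rates and the crude risks in Annex 5, Tables 4 and 5, would then all err towards persistence. Leaving the event undated lets two analysts obtain different curves and rates from the same data. The 30- and 90-day analyses would also move the last detectable stop, so their absolute results would mix a change of gap rule with a change of horizon.

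**Working it through.** The plan gives no expected discontinuation rate, so there is no figure of its own to reproduce. Its dates and counts are consistent: 21 May 2015 + 180 days = 17 November 2015, and 3,889 + 10,862 = 14,751.

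**1. Entry days that cannot yield an event.** 17 November 2015 to 31 March 2018 is 866 days inclusive. Section 9.7.2 gives 30 days as the usual supply of Stiolto; the same is assumed for Anoro. The earliest recordable event is at day 30 + 60 = 90. Entry after 31 December 2017 leaves fewer than 90 days of data, which covers 90 entry days: 90/866 = 10.4%, or about 1,533 of 14,751 if entry is uniform. The Third Year of entry in the Abstract and Annex 5, Table 2 (1 December 2017 to 31 March 2018) has 121 days, of which 90 (74%) cannot yield an event.

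**2. Last detectable stop for a patient with full follow-up.** This is 365 minus the grace period: day 335, 305 or 275 for 30, 60 or 90 days.

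**3. One assumed scenario.** The inputs are not in the documents: 30-day fills, 25% stop after the first fill and 8% after each later one, uniform entry, no death or disenrollment.

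- True persistence at day 365 (12 supplies): 0.75 × 0.92^11 = 0.300.
- Gap-end dating: a stop must occur by day 305 (10 supplies), so 0.75 × 0.92^9 = 0.354. This is the true curve shifted by 60 days.
- Supply-end dating: the curve is flat after day 300, and patients cut off by end of data stay in the risk set for up to 60 days in which their stop could not be recorded. Kaplan-Meier persistence is 0.39.
- Crude risk: 90 entry days give 0. The next nine blocks of 30 days give 0.250, 0.310, 0.365, 0.416, 0.463, 0.506, 0.545, 0.582 and 0.615 (sum 4.052). The other 506 days give 1 − 0.354 = 0.646. So (30 × 4.052 + 506 × 0.646)/866 = 0.52, against a true 0.70.
- Discontinuation rate (simulated): about 1,307 per 1,000 person-years becomes 947 with gap-end dating, which adds 60 off-drug days per stopper, or 1,121 with supply-end dating.

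**4. A range of true risks.** Simulation with 40,000 patients per arm, a constant stop probability per fill and otherwise the same assumptions:

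| True one-year risk | Crude risk, literal rule | 1 − KM, supply end | 1 − KM, gap end | 1 − KM after the changes |
|---|---|---|---|---|
| 30% | 19% | 23% | 25% | 30% |
| 50% | 33% | 41% | 44% | 50% |
| 70% | 49% | 60% | 64% | 70% |

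The last column uses supply-end dating, claims after day 365, and censoring 60 days before data end. Entry was not closed early.

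**5. Relative measures.** With the same entry pattern in both arms, a true hazard ratio of 0.8 returned 0.79 to 0.81 under either dating. With no true difference and one arm's entry skewed moderately or strongly late, supply-end dating gave an unadjusted hazard ratio of about 0.96 to 0.97 or 0.91 to 0.92. Stratifying on three entry years gave 0.995 or 0.98, and on two years 0.99 or 0.96. Gap-end dating gave about 1.00. The crude risk in the late arm fell from 52% to 47% or 42%, a null risk ratio of 47/52 = 0.90 or 42/52 = 0.81. Those last figures are before matching and include ordinary incomplete follow-up.

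**The case against.** The strongest reply is that the primary objective is relative persistence in the matched cohort, and absolute rates are secondary. That stands. A reader might infer that the hazard ratio favours Stiolto because it was approved later. The documents do not support this: they give no entry dates by arm, entry opens 180 days after Stiolto's approval, and entry year is in the propensity model. The residual null bias in step 5 needs supply-end dating and invented entry skews. It is somewhat larger with the two entry-year levels of Section 9.3.3 than with the three in the Abstract and Annex 5, so those lists should agree.

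Second, gap-end dating is a legitimate convention. Late entry then becomes ordinary administrative censoring, which Kaplan-Meier and Cox handle, and the curve shifts by a known 60 days. That also stands, but the plan does not state it, the day-365 value would describe stops by about day 305, and the crude risk stays too low.

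Third, the words on follow-up may qualify discontinuation without requiring the whole gap to fit under the cap, and nothing expressly forbids using later claims. So the day-365 limit is the literal reading and not a certainty. The end-of-data limit does not depend on it: with later claims allowed but data ending on 31 March 2018, crude risk in the step 4 scenarios is still 21%, 37% and 53% against 30%, 50% and 70%.

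Fourth, the grace-period analyses report Tables 2, 4 and 5 and no curve, so their hazard ratios remain informative. The horizon problem applies to their rates and risks.

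**Conclusion.** The point holds for absolute persistence and should be fixed. Under the literal rule, the curve, the rates and above all the crude risk err towards persistence. In the scenario of step 3, one-year persistence is overstated by about 5 points with gap-end dating (0.354 against 0.300) or 9 points with supply-end dating, and crude risk is understated by about 18 points. These sizes rest on assumed stop patterns, 30-day fills and uniform entry. The 866-day window follows from the plan's dates alone, and the 90-day no-event span adds only the 30-day fill.

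The primary matched hazard ratio is little affected: about 1.00 under the null with gap-end dating, and only modestly biased with supply-end dating if entry dates differ by arm within entry-year strata. The logistic relative risks in Section 9.7.1.3 score censored patients as non-events, so they are more exposed to such a difference. None of this shows that the comparison is biased towards either product.

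**What to change.** In Sections 9.2.1, 9.3.2.1 and 9.7.1.2:

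1. Date discontinuation at the end of the last days' supply.
2. Use claims for the full grace period after day 365 to confirm gaps that open by day 365.
3. Censor at the earliest of day 365, death, disenrollment minus the grace period, and 31 March 2018 minus the grace period. State how a gap left incomplete by death is handled.
4. Report one-year risk as 1 minus Kaplan-Meier in place of crude events over all entrants.
5. Apply the same rules with the 30- and 90-day grace periods, so that the horizon stays at 365 days.

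Closing entry on 31 December 2017 is not needed: items 1 to 3 recovered the assumed 30% in the step 3 scenario at all three grace lengths with entry left open.

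The work is wording and programming on existing data. With the 60-day grace period, up to 60 days of follow-up is lost for patients censored early by disenrollment or data end, and entrants in the last 60 days contribute no person-time.
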